2.2. SECONDARY OBJECTIVES

The secondary objectives are :

- To assess the immunogenicity of Hib-components in terms of percentage of subjects above the thresholds for short-term (0.15 µg/mL) and long-term (1.0 µg/mL) protection as well as in terms of GMCs (post-primary, pre- and post-booster vaccination).
- To assess the safety of *Infanrix hexa* and *Vaxelis* co-administered with *Prevenar 13* in terms of unsolicited adverse events (AEs) and serious adverse events (SAEs).

2.3. TERTIARY/EXPLORATORY OBJECTIVES

The exploratory/tertiary objective is:

CCI

- The tertiary objective may be reported separately.

2.4. ENDPOINTS

Table A: List of Endpoints

Objectives	Endpoints	Definition	Analysis set
Co-primary	Non-inferiority: Anti-PRP antibody concentration $\geq 5\mu\text{g/mL}$ at 1-month post-booster vaccination	
 • GMCs o Criterion: Lower limit (LL) of the 2-sided 95% confidence interval (CI) on group GMC ratio (Inv_group over Com_group) is above 0.5. • Percentage of subjects with anti-PRP antibody concentrations $\geq 5\mu\text{g/mL}$ at 1-month post booster vaccination o Criterion: First primary objective is met 	Per protocol set (PPS)

Document : \quintiles.net\enterprise\Apps\sasdata\SASb\SAS\GSK\Infanrix\PPD \Biostatistics\Documentation\NSAP

Author: PPD Version Number: 1.0

Version Date: [07JAN2021]

Template No.: CS_TP_BS016 Revision 6

Reference: CS_WI_BS005

Effective Date: 02Dec2019

		and the LL of the 2-sided 95% CI on group difference in the percentage (Inv_group minus Com_group) is above -10%.	
	Superiority: Anti-PRP antibody concentration $\geq 5\mu\text{g/mL}$ at 1-month post-booster vaccination	
 • GMCs o Criterion: All previous objectives are met and the LL of the 2-sided 95% CI on group GMC ratio (Inv_group over Com_group) is above 1. • Percentage of subjects with anti-PRP antibody concentrations $\geq 5\mu\text{g/mL}$. o Criterion: All previous objectives are met and the LL of the 2-sided 95% CI on group difference in the percentage (Inv_group minus Com_group) is above 0. 	Exposed Set (ES)
Secondary	Anti-PRP antibody concentrations at 1-month post-primary vaccination, pre-booster and 1-month post-booster vaccination.	Percentage of subjects above the thresholds for short-term (0.15 $\mu\text{g/mL}$) and long-term (1.0 $\mu\text{g/mL}$) protection as well as in terms of GMCs (post-primary, pre- and post-booster vaccination)	ES & PPS
	Occurrence of unsolicited AEs during the 31-day (Days 1-31) follow-up period after each vaccination.	Percentage of subjects with any unsolicited AEs (including all SAEs) during the 31-day (Days 1-31) follow-up period after each vaccination	ES
	Occurrence of SAEs after first dose up to study end.	Percentage of subjects with SAEs throughout the study period.	ES
Tertiary/Exploratory	CCI		ES & PPS

Document : \quintiles.net\enterprise\Apps\sasdata\SASb\SAS\GSK\Infanrix\PPD \Biostatistics\Documentation
n\SAP

Author: PPD Version Number: 1.0

Version Date: [07JAN2021]

Template No.: CS_TP_BS016 Revision 6

Reference: CS_WI_BS005

Effective Date: 02Dec2019

		CCI	
--	--	-----	--

3. STUDY DESIGN

3.1. GENERAL DESCRIPTION

Approximately 500 subjects will be randomised/vaccinated in a 1:1 ratio. They will be randomised to 2 parallel groups of subjects:

- Inv_group (Investigational group): All subjects in this group will receive 3 doses (2 primary doses+1 booster dose) of *Infanrix hexa* co-administered with 3 doses of *Prevenar 13* at 2, 4, and 12 months.
- Com_group (Comparator group): All subjects in this group will receive 3 doses (2 primary doses+1 booster dose) of *Vaxelis* co-administered with 3 doses of *Prevenar 13* at 2, 4, and 12 months.

The intended duration of the study per subject is approximately 11 months, divided into 2 study phases.

- Study phase 1: Primary study phase, starting at Visit 1 (Day 1) and ending at Visit 3 (Month 3); i.e., 1 month following the second primary dose.
- Study phase 2: Booster study phase, starting at Visit 4 (Month 10) and ending at Visit 5 (Month 11); i.e., 1 month after the booster dose.

For more information, see Section 4.0 of the Protocol.

Table B: Treatment Group, Treatment and Dosing

Study Phase	Type of Contact and Timepoint	Treatment Group	Treatment Name	# of Doses	Age of subjects
Phase 1 (Primary)	Visit 1 Day 1	Inv_group (Investigational group)	Infanrix hexa	1 (PRI)	2 months
			Prevenar 13™	1 (PRI)	
		Com_group	Vaxelis	1 (PRI)	

Document : \quintiles.net\enterprise\Apps\sasdata\SASb\SAS\GSK\Infanrix\PPD\Biostatistics\Documentation\NSAP

Author: PPD Version Number: 1.0

Version Date: [07JAN2021]

Template No.: CS_TP_BS016 Revision 6

Reference: CS_WI_BS005

Effective Date: 02Dec2019

		(comparator group)	Prevenar 13™	1 (PRI)	
Phase 1 (Primary)	Visit 2 Month 2	Inv_group (Investigational group)	Infanrix hexa	1 (PRI)	4 months
			Prevenar 13™	1 (PRI)	
		Com_group (comparator group)	Vaxelis	1 (PRI)	
			Prevenar 13™	1 (PRI)	
Phase 2 (Booster)	Visit 4 Month 10	Inv_group (Investigational group)	Infanrix hexa	1 (BST)	12 months
			Prevenar 13™	1 (BST)	
		Com_group (comparator group)	Vaxelis	1 (BST)	
			Prevenar 13™	1 (BST)	

PRI=primary, BST=booster

 Document: \quintiles.net\enterprise\Apps\sasdata\SASb\SAS\GSK\Infanrix\PPD\Biostatistics\Documentation
 Author: PPD

Version Number: 1.0

Version Date: [07JAN2021]

[figure not shown]
Template No.: CS_TP_BS016 Revision 6

Reference: CS_WI_BS005

Effective Date: 02Dec2019

Figure A: Study Schema

Randomisation (1:1)

Visits (V):

V1 V2 V3 V4 V5

Timepoints: Day 1 Month 2 Month 3 Month 10 Month 11

Age of the subjects: 2 Months 4 Months 5 Months 12 Months 13 Months

Blood samples: Post-PRI Pre-BST Post-BST

BST=booster, PRI=primary

3.2. SCHEDULE OF EVENTS

Schedule of events can be found in Section 1.3 of the Protocol.

3.3. CHANGES TO ANALYSIS FROM PROTOCOL

Given the current climate with COVID-19 pandemic, additional analyses for subjects diagnosed with COVID-19 will be performed. This will be assessed on a case by case basis (e.g., adapted missing data imputation techniques, subgroup analyses to explore the indirect or direct impact of COVID-19) and discussed in an SAP addendum as needed.

Document : \\quintiles.net\enterprise\Apps\sasdata\SASb\SAS\GSK\Infanrix\PPD \Biostatistics\Documentation\NSAP

Author: PPD Version Number: 1.0

Version Date: [07JAN2021]

Template No.: CS_TP_BS016 Revision 6

Reference: CS_WI_BS005

Effective Date: 02Dec2019

4. PLANNED ANALYSES

The following analyses will be performed for this study:

- Final Analysis

4.1. DATA MONITORING COMMITTEE (DMC)

There will be no DMC planned for this study.

4.2. INTERIM ANALYSIS

There will be no interim analysis planned for this study.

4.3. FINAL ANALYSIS

All final, planned analyses identified in this SAP will be performed by IQVIA Biostatistics following GlaxoSmithKline Biologicals SA authorization of this Statistical Analysis Plan, Database Lock, Sponsor Authorization of Analysis Sets and Unblinding of Intervention.

5. ANALYSIS SETS

Agreement and authorization of subjects included/excluded from each analysis set will be conducted prior to the unblinding of the study.

5.1. PROCESS FOR ANALYSIS SET ASSIGNMENT

- Definitions for analysis sets are provided below.
- Prior to database lock, a transfer of raw data from the eCRF will occur, and subjects will be assigned to analysis sets in accordance with the definitions in this SAP and the available data at that time. However, the protocol deviations will be monitored continuously throughout the study.
- Listings presenting subjects excluded from each preliminary analysis set and reasons for exclusion will be prepared for sponsor review ahead of database lock in order to allow appropriate related data

Document : \\quintiles.net\enterprise\Apps\sasdata\SASb\SAS\GSK\Infanrix\PPD\Biostatistics\Documentation\NSAP

Author: PPD Version Number: 1.0

Version Date: [07JAN2021]

Template No.: CS_TP_BS016 Revision 6

Reference: CS_WI_BS005

Effective Date: 02Dec2019

queries to be issued.

- Listings presenting subjects excluded from each final analysis set and reasons for exclusion will be prepared for sponsor review ahead of unblinding for a final review and approval. However, for deviations that can only be assessed after unblinding (such as vaccination errors or pre and post booster samples), these will be reviewed after unblinding.
- A Data Review meeting will be held to confirm analysis set assignment for each subject and any changes will be recorded. Changes will be implemented, and an updated analysis set assignment will be approved by the sponsor.
- Sponsor authorization of the analysis sets will be necessary to unblind the data after database lock. Once approved, analysis sets will be finalized, and the database will be locked.
- After database lock, the final analysis sets will be derived using the final study data, i.e., clinical database (CRF), external vendor data (immunogenicity results) and protocol deviations log.

5.2. ENROLLED SET [ENR]

The enrolled set (ENR) will include all subjects with a study intervention (either randomised or vaccinated or with a blood draw).

5.3. EXPOSED SET [ES]

The exposed set (ES) will include all vaccinated subjects with ICF and exclude any fraudulent data. Subjects will be analysed according to the intervention they received at Dose 1.

5.4. PER PROTOCOL SET [PPS]

The per protocol set (PPS) will include all eligible subjects from the exposed set who received all study vaccines as per protocol, who had anti-PRP results post-vaccination, who complied with vaccination/blood draw intervals, without intercurrent conditions that may interfere with immunogenicity and without prohibited concomitant medication/vaccination. Subjects will be analysed according to the intervention they received at Dose 1. Refer to Section 6.2 for details on the intervals.

More specifically, the analysis at 1 month post-booster vaccination based on the PPS will include all eligible subjects:

Document : \quintiles.net\enterprise\Apps\sasdata\SASb\SAS\GSK\Infanrix\PPD\Biostatistics\Documentation\NSAP

Author: PPD Version Number: 1.0

Version Date: [07JAN2021]

Template No.: CS_TP_BS016 Revision 6

Reference: CS_WI_BS005

Effective Date: 02Dec2019

- who received all the study vaccines up to booster dose as per the vaccination schedule and for whom administration route of study vaccines up to booster dose was as per protocol;
- who did not receive a medication/product before the blood sampling at Visit 4 (Month 10) which led to elimination from PPS;
- who did not present with a contraindication before the blood sampling at Visit 4 (Month 10) which led to elimination from PPS;
- who complied with the post-booster blood sample schedule, i.e. 21-48 days post-booster vaccination;
- who were not administered a vaccine not foreseen by the study protocol before the corresponding post-vaccination blood sample collection;
- who had immunogenicity results at 1-month post-booster vaccination;

Likewise, the analysis at 1 month post-dose 2 based on the PPS will include all eligible subjects:

- who received all the study vaccines up to second dose as per the vaccination schedule and for whom administration route of study vaccines up to second dose was as per protocol;
- who did not receive a medication/product before the blood sampling at Visit 3 (Month 5) which led to elimination from PPS;
- who did not present with a contraindication before the blood sampling at Visit 3 (Month 5) which led to elimination from PPS;
- who complied with the post-primary blood sample schedule, i.e. 21-48 days post-dose 2 vaccination;
- who were not administered a vaccine not foreseen by the study protocol before the corresponding post-dose 2 vaccination blood sample collection;
- who had immunogenicity results at 1-month post-dose 2 vaccination;

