**Table 7 Analysis Sets**

Analysis Set	Description
Enrolled set	All subjects with a study intervention (either randomised or vaccinated or with a blood draw).
Exposed set (ES)	All vaccinated subjects. Subjects will be analysed according to the intervention they received at Dose 1.
Per protocol set (PPS)	All eligible subjects who received all DTPa-combination study vaccines as per protocol, who had anti-PRP results post-vaccination, who complied with vaccination/blood draw intervals ( Table 8 ), without intercurrent conditions that may interfere with immunogenicity and without prohibited concomitant medication/vaccination. Subjects will be analysed according to the intervention they received at Dose 1.

**Table 8** Intervals Between Study Visits

Interval	Length of interval	Allowed interval
Birth (age is 0 day on birth date) → Visit 1	6 to 12 weeks	42 to 84 days
Visit 1 → Visit 2	60 days	52, 78 days
Visit 2 → Visit 3	30 days	21, 48 days
Birth → Visit 4	365 days	335, 395 days
Visit 4 → Visit 5	30 days	21, 48 days

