16.2.1. SECONDARY IMMUNOGENICITY VARIABLES & DERIVATIONS

In order to assess the immunogenicity of Hib-components in terms of percentage of subjects above the thresholds for short-term ($\geq 0.15 \mu\text{g/mL}$) and long-term ($\geq 1.0 \mu\text{g/mL}$) protection as well as in terms of GMCs (post-primary, pre- and post-booster vaccination):

Document : \quintiles.net\enterprise\Apps\sasdata\SASb\SAS\GSK\Infanrix\PPD\Biostatistics\Documentation\NSAP

Author: PPD Version Number: 1.0

Version Date: [07JAN2021]

Template No.: CS_TP_BS016 Revision 6

Reference: CS_WI_BS005

[figure not shown]
Effective Date: 02Dec2019

- Descriptive analysis for each treatment group will be provided by country and maternal immunisation for anti-PRP antibody concentrations at 1-month post-primary vaccination, pre-booster and 1-month post-booster vaccination for the PPS and ES. This analysis will also be provided per subgroup for the PPS as per Section 7.5.
- GMC and its associated 2-sided 95% CI will be calculated on all subjects by treatment groups at 1-month post-primary, pre-booster and 1-month post-booster vaccination.
- The number and percentage of subjects with anti-PRP antibody concentrations $\geq 0.15 \mu\text{g/mL}$, $\geq 1.0 \mu\text{g/mL}$, $\geq 5.0 \mu\text{g/mL}$ at 1-month post-primary, pre-booster and 1-month post-booster vaccination with associated 2-sided 95% CI will be provided by treatment groups. [Clopper](#) and Pearson exact CI will be used for proportions.
- An adjusted GMC and GMC ratio with 2-sided 95% CI for treatment group which is derived from an ANOVA model on log10 transformed concentration will be tabulated for anti-PRP antibody concentrations. The model will include country, maternal immunisation and group as fixed effects.
- Reverse cumulative curves at each time point will also be displayed by treatment group for the ES and PPS.

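### SAP 5.4 intends a per-protocol set for each time point, but its texts disagree on Visit 3 timing, the exclusion cut-off, the pre-booster set and the vaccines required

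*SAP*

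**What the plan says.** **General definition.** Protocol Table 7 describes one PPS with no time point: "All eligible subjects who received all DTPa-combination study vaccines as per protocol", and "who had anti-PRP results post-vaccination, who complied with vaccination/blood draw intervals". It refers to Protocol Table 8 for the intervals, and that table includes Visit 2 to Visit 3 (21 to 48 days). The set also requires no interfering intercurrent condition and no prohibited medication or vaccination. SAP 5.4 opens in nearly the same way but asks for "eligible subjects from the exposed set who received all study vaccines as per protocol", and sends the reader to SAP 6.2 for the intervals. SAP 6.2 gives an example in which a child whose post-dose 2 sample is drawn one day too early is eliminated, with no limit to a particular analysis.

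**Time-point lists.** SAP 5.4 then continues: "More specifically, the analysis at 1 month post-booster vaccination based on the PPS will include all eligible subjects" who meet six bullets. The only draw interval named is for those "who complied with the post-booster blood sample schedule, i.e. 21-48 days post-booster vaccination". The medication bullet reads "who did not receive a medication/product before the blood sampling at Visit 4 (Month 10) which led to elimination from PPS", and the contraindication bullet has the same Visit 4 limit. The parallel post-dose 2 list needs only children "who received all the study vaccines up to second dose as per the vaccination schedule", and stops its medication and contraindication bullets at its own Visit 3 sample.

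**Use.** Protocol 9.4.3 and SAP 16.1.1 place non-inferiority on the PPS and superiority on the Exposed Set (ES). SAP 16.2.1 plans descriptive analyses of "anti-PRP antibody concentrations at 1-month post-primary vaccination, pre-booster and 1-month post-booster vaccination for the PPS and ES". SAP 3.3 declares only COVID-19 analyses as changes from the protocol.

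**The concern.** The PPS is the only set named for objectives 1 and 2, and SAP 7.4 allows no superiority conclusion unless both are met. A programmer who follows the general sentence and one who follows the post-booster list would build different sets from the same data.

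The choice should not stay open late. SAP 5.1 lets some deviations, including those concerning pre- and post-booster samples, be reviewed after unblinding.

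For the earlier time points, applying the general sentence literally would make a post-primary or pre-booster result depend on whether the child later received the booster and attended Visit 5 on time.

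**Working it through.** **1. Membership under each text.** The children below are illustrative.

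| Child | General definition | Time-point list |
|---|---|---|
| A: all doses on schedule, valid Visit 5 sample, Visit 3 sample 50 days after dose 2 | Out, since 50 > 48 (Protocol Table 8, SAP Table C) | In the post-booster set; no Visit 3 criterion |
| B: complies otherwise, but takes an eliminating medication between Visits 4 and 5 | Out | Not removed by the post-booster list; its cut-off is Visit 4 |
| C: doses 1 and 2 and Visit 3 sample valid, then withdraws | Out, no booster | In the post-dose 2 set |
| D: valid Visit 4 sample, then Visit 5 out of window | Out | No pre-booster list exists |
| E: all hexavalent doses given, one *Prevenar 13* dose missed | Table 7: not removed on this ground. SAP opening: removed on a plain reading | Removed on a plain reading; the list also refers to all study vaccines |

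On child B, another bullet of the post-booster list, on vaccines not foreseen by the protocol, runs to the corresponding post-vaccination sample. Two bullets therefore stop one visit short of a third in the same list, and the post-dose 2 list has no such gap. On child E, the Protocol glossary counts a concomitantly administered vaccine as a study vaccine.

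**2. The plan's own figures.** Inputs from Protocol 9.2: 400 evaluable (200 per group), 20% not evaluable, one-sided 2.5%, log10 variance 0.63, GMC ratio 1.75 (0.243 in log10) with margin 0.5 (0.301 in log10), and 62% versus 46% with margin 10 points.

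- Enrolment: 400 / (1 − 0.20) = 500, as stated.
- GMC non-inferiority: noncentrality = (0.243 + 0.301) / (√0.63 × √(2/200)) = 0.544 / 0.0794 = 6.85. Power is above 99.9%, which agrees with the stated figure of more than 99%.
- Percentage non-inferiority (unpooled normal approximation to the Miettinen-Nurminen test): SE = √[(0.62×0.38 + 0.46×0.54)/200] = √(0.484/200) = 0.0492. Then z = 0.26/0.0492 − 1.96 = 3.33, so power is 99.96%. This also agrees.

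**3. If the stricter text removes more children.** The documents give no rate of out-of-window Visit 3 draws. Assume 2%, 5% or 10% of the 200 per group.

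| Removed | n per group | Children out of 400 | Power, GMC | Power, percentage | 95% half-width, percentage |
|---|---|---|---|---|---|
| 0% | 200 | 0 | >99.9% | 99.96% | 9.6 points |
| 2% | 196 | 8 | >99.9% | 99.95% | 9.7 points |
| 5% | 190 | 20 | >99.9% | 99.93% | 9.9 points |
| 10% | 180 | 40 | >99.9% | 99.89% | 10.2 points |

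The half-width is 1.96 × √(0.484/n).

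**4. Post-primary and pre-booster.** The largest loss consistent with the planning assumption is all 20% of non-evaluable children, 250 down to 200 per group. The interval on the log10 GMC ratio then widens by √(250/200) = 1.118, or 12%, whatever the SD. With 0.63 as the variance, the half-width 1.96 × √0.63 × √(2/n) goes from 0.139 to 0.156. This is an upper bound: some non-evaluable children will be ineligible or have no sample, and no rule would recover them.

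**The case against.** The best defence is that the lists specify the general sentence rather than compete with it. They are introduced as specifications, and SAP 7.5 speaks of the PPS at the post-booster time point, which makes sense only if membership varies by time point. Compliance with intervals can then be read as compliance with those that matter for the sample analysed. This stands as evidence of intent. It does not settle child A, because the SAP 6.2 example eliminates without limit, nor child B, whose cut-off is fixed by the list itself.

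A reader might infer that the lists drop the intercurrent-condition exclusion, since neither repeats it. The documents do not support that: the opening sentence of SAP 5.4 still carries it, and nothing repeals it. A reader might also infer that Table 7 excludes a child with no Visit 3 sample. It asks only for post-vaccination results, which a Visit 5 result can satisfy; the clear conflict is over a Visit 3 draw that is out of window.

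Protocol 9.4 leaves the description of analysis sets to the SAP, so adding time-point detail is not in itself an undeclared change. That is fair. It covers less well a change in which vaccines are required.

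The secondary analyses are descriptive and are also run on the ES, so earlier titres are not lost to the report. SAP 5.1 also requires exclusion listings, a data review meeting and sponsor authorisation before unblinding. These steps apply a rule but do not supply one, and SAP 5.1 leaves an exception for deviations that can be assessed only after unblinding.

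**Conclusion.** The point holds as a defect of specification in a confirmatory set. Four things need settling: Visit 3 timing, the Visit 4 cut-off in the post-booster list, the missing pre-booster list, and the vaccines required. The Visit 4 cut-off is wrong on its face, since an event between Visits 4 and 5 precedes the measured outcome.

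It would be tempting to conclude that the non-inferiority result is at risk or that the texts are irreconcilable. Neither follows. Under the plan's assumptions, non-inferiority power stays above 99% across the assumed 2% to 10% range, and the half-width for the percentage difference moves by at most about 0.5 points. Outside those assumptions, with both groups at 50%, power for the percentage would be 51.6% at 200 per group and 47.5% at 180, but the plan does not posit that case. The 12% widening for earlier time points is a ceiling on descriptive results.

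The change is worth making for two reasons: the gating set is fixed unambiguously before unblinding, and earlier results are not conditioned on later attendance.

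**What to change.** In SAP 5.4:

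- State that PPS membership is set per time point. The general criteria, including intercurrent conditions and prohibited medication or vaccination, apply to events up to the analysed sample, and only the doses and intervals relevant to that sample count.
- In the post-booster list, move the medication and contraindication cut-off from the Visit 4 sample to the Visit 5 sample.
- State that Visit 3 timing, or a missing Visit 3 sample, does not exclude a child from the post-booster PPS.
- Add a pre-booster list: doses 1 and 2 per schedule, Visit 4 sample taken before the booster and within the SAP Table C window, and a result available.

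In SAP 6.2, limit the worked example to the post-primary PPS. Reconcile Protocol Table 7 with the SAP on which vaccines are required, and note the change in SAP 3.3. The same edit can correct the Visit 3 label in SAP 5.4, which gives Month 5 where the study timeline has Month 3 (age 5 months).

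The cost is SAP wording and one more analysis-set flag before unblinding. No new data are needed. The PPS count will differ slightly by time point and should be reported that way.
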